Date of the document: November 25th, 2021

Clinical follow-up of Anti-Carbamylated Antibody Status in Rheumatoid Arthritis patients at 6, 12 and 18 months

Concept

Patients with rheumatoid arthritis with positive antibodies against carbamylated proteins (anti-CarP) have a more severe clinical course

Background

The immune based pathophysiology of rheumatoid arthritis is one of the most studied. We already know that the citrullinated peptide antigen inducing antibody formation and subsequent [LVG1] anti-cyclic citrullinated peptide (anti-CCP). In some patients this can explain the clinical manifestations. However it is also apparent in some groups of patients with rheumatoid arthritis who do not have anti-CCP antibodies. It is possible that there is the presence of a variety of antigens exposed during the disease, and perhaps different clinical presentations associated with each of them.

The use of anti-CCP has been included in the classification criteria of rheumatoid arthritis developed by the American College of Rheumatology in 2010 and generated the presence of two sub-groups of patients with rheumatoid arthritis, the positive and negative for anti-CCP. It is very important to study the presence of anti-CCP antibodies in rheumatoid arthritis patients because they influence the clinical behavior and response to treatment. In very early or undifferentiated arthritis, the presence of anti-CCP antibodies can predict the presence of erosions in the course of the disease. On the other hand, patients with anti-CCP tend to have better responses to treatment with methotrexate.

Initially it was thought that the obvious pathophysiological link between rheumatoid arthritis and citrullinated peptides leading to formation of antibodies was the apparent cause of the clinical manifestations, but soon it was demonstrated that there were groups of patients with clinical manifestations of rheumatoid arthritis that did not have anti-CCP antibodies so its genesis was not explained by citrullination. Then it is plausible to find a diversity of antigens exposed during the illness and perhaps different clinical presentations associated with each one or its combinations. So, some studies are attempting to show other possible antigens involved in rheumatoid arthritis and one of them uses homocitrulline as an antigenic basis to rheumatoid arthritis pathophysiology. The carbamylation or homocitrullination is a posttranslational modification of proteins that occurs when the amino acid lysine reacts with cyanate in a nonenzyme-mediated process generating homocitrulline. Mydel, Bokarewa and cols. demonstrated that immunization of mice with homocitrulline- and citrulline-containing peptides leads to development of erosive arthritis following intra-articular injection of homocitrulline-containing peptides and proposed that homocitrulline induced activation of T cells is a key mechanism in the pathogenesis of autoimmune arthritis as it serves as an initial triggering event for neo-epitope recognition of citrulline containing peptides. Recently It has been shown that rheumatoid arthritis patients have homocitrullinated proteins in their joints which can trigger an inflammatory response with formation of antibodies against homocitrulline.

Shi et al. showed in a study of 571 rheumatoid arthritis patients and 350 healthy subjects the following statements:

- Anti-CarP antibodies are different from anti-cyclic citrullinated peptide and they do not cross-react.
- The Anti-CarP antibodies are present in sera of patients with rheumatoid arthritis.
- Anti-CarP antibodies are found in sera of patients without anti-CCP.
- The Anti-CarP antibodies are associated with increased progression to radiographic damage.

Thus, anti-CarP antibodies are a promising new serological marker for anti-CCP negative Rheumatoid Arthritis and are associated with a more severe clinical course.

Hypothesis

Patients with rheumatoid arthritis with positive antibodies against carbamylated proteins

(anti-CarP) have a more severe clinical course and elevated cardiovascular risk.

Design

It is a parallel study for clinical follow-up, observational.

Description of Subject Population(s)

- Patients older than 18 years old, both genders, with rheumatoid arthritis diagnosis according to ACR EULAR 2010 classification that accepted and signed informed consent that were seen at the Rheumatology Clinic in Hospital Universitario "[name] González", Monterrey, NL. México.
- Exclusion: Chronic kidney disease and pregnant patients

Assessment Tools and Procedures

- DAS-28 VSG
- Lipid profile

Length of Study in Months

• 18

Primary Endpoints

• Clinical activity measured by DAS28-VSG in patients with rheumatoid arthritis according to antibodies against carbamylated proteins (anti-CarP) status at 6, 12 and 18 months

Secondary Endpoints

- Number and accumulative dose of DMARDs according to antibodies against carbamylated proteins (anti-CarP) status at 6, 12 and 18 months
- Cardiovascular risk according to antibodies against carbamylated proteins (anti-CarP) status at 6, 12 and 18 months

Clinical Information

- Total number of subjects 262
- Number of subjects for each treatment arm 131
- Study Duration Per Patient (in Months) 18

Primary Objective

The primary objective of this study in adult subject with RA is as follows:

1. To explore the clinical differences in activity indexes (DAS28-VSG) at 6, 12 and 18 months of follow up according the anti-CarP status

Study Secondary Objective(s)

- To investigate the remission rate (DAS28-VSG) according the anti-CarP status
- To compare the percentage of subjects with DAS28-VSG LDA at 6, 12 and 18 months according the anti-CarP status
- To compare the accumulative dose of prednisone between groups according the anti-CarP status
- To compare the number and doses of DMARD's used to treat RA between groups according the ant CarP status

Study Design

- Prospective, Non-Randomized, Open Label
- Inception Cohort Study

Study Primary Efficacy Endpoints

The primary efficacy endpoints is as follows:

• The percentage of subjects who meet DAS28-VSG < 2.6 at 6, 12 and 18 months in the Anti CarP+ve arm compared Anti CarP-ve arm

Study Secondary Efficacy Endpoints

The secondary efficacy endpoints are as follows:

- Percentage of subjects with DAS28-VSG LDA at 6, 12 and 18 months at 6, 12 and 18 months in the Anti CarP+ve arm compared Anti CarP-ve arm
- Median of the cumulative dose of prednisone at 18 months at 6, 12 and 18 months in the Anti CarP+ve arm compared Anti CarP-ve arm

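### The protocol calls the cohort open label and does not say who sees the anti-CarP result or when, so DAS28 may be scored with serostatus known

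*Protocol*

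**What the plan says.** The Design section of the protocol describes the study in these words: "It is a parallel study for clinical follow-up, observational". The later Study Design section adds "Prospective, Non-Randomized, Open Label". The groups compared are the two antibody serostatus groups, which the protocol calls arms; the Clinical Information section gives "Number of subjects for each treatment arm 131".

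The primary efficacy endpoint is "The percentage of subjects who meet DAS28-VSG < 2.6 at 6, 12 and 18 months in the Anti CarP+ve arm compared Anti CarP-ve arm". The secondary objectives include two that depend on prescribing: "To compare the accumulative dose of prednisone between groups according the anti-CarP status" and "To compare the number and doses of DMARD's used to treat RA between groups according the ant CarP status".

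The expected direction is stated in advance. On patients with positive antibodies, the Hypothesis reads "anti-CarP) have a more severe clinical course and elevated cardiovascular risk".

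The protocol does not say when serum is drawn or assayed, where the assay is run, who receives the result, or whether the DAS28 assessor, the patient or the prescriber is kept unaware of it.

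**The concern.** The exposure is a laboratory result, so nothing in the design requires the assessor to know it. The outcome is less objective. The protocol does not list the components of DAS28-VSG. In its standard form the index combines tender and swollen joint counts, a patient global rating and the sedimentation rate, and only the last is a laboratory value. The endpoint then cuts the index at 2.6, so a small shift in scoring near the cut-off changes a patient's outcome.

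Knowledge of status could act in two directions. An assessor or patient who expects positives to do worse may score them higher, which would create or enlarge a difference in remission. A prescriber who knows the result may treat positives differently. That could shrink a real DAS28 difference and at the same time produce one in the prednisone and DMARD comparisons. A statistical analysis plan cannot supply masking after the visits have taken place.

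**Working it through.** **1. The plan's own figure.** Inputs from Study Sample Size Calculation: remission at 12 months 33% (positive) and 50% (negative), two-sided alpha 0.05, beta 0.2. With the pooled formula and no continuity correction:

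n = [1.960·√(2·0.415·0.585) + 0.842·√(0.33·0.67 + 0.50·0.50)]² / 0.17² = (1.366 + 0.578)² / 0.0289 = 130.7, so 131 per group.

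This matches the stated 131. The continuity-corrected formula gives 143. That discrepancy is a separate matter. Here 131 per group is taken as given, with the continuity-corrected test that the section names.

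**2. Bias that creates a difference.** Assumptions, none of them in the protocol: DAS28 is normally distributed with SD 1.2 to 1.4; true remission is 50% in both groups; every positive patient's score is raised by the same amount s. Observed remission in positives is then Φ(−s/SD). The rejection rate comes from exact binomial enumeration at 131 v 131.

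| Shift s | Observed remission, positives | Rejection rate, continuity-corrected | Rejection rate, uncorrected |
|---|---|---|---|
| 0 | 50% | 4.1% | 5.5% |
| 0.1 | Φ(−0.1/1.2) = 46.7% to Φ(−0.1/1.4) = 47.2% | 6.3-7.1% | 8.1-9.1% |
| 0.2 | Φ(−0.2/1.2) = 43.4% to Φ(−0.2/1.4) = 44.3% | 13.2-16.7% | 16.1-20.0% |

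**3. Bias that hides a difference.** Suppose the planned 33% v 50% is true, and status-driven treatment raises remission in positives by 3 or 5 points, to 36% or 38%. Exact power at 131 per group falls from 77% to 59% or 46% with the continuity-corrected test, and from 81% to 64% or 51% without the correction. The 3 and 5 points are also assumptions.

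**4. A check on proportion.** For scoring bias alone to produce the planned gap of 50% v 33%, the shift must satisfy Φ(−s/SD) = 0.33, so s = 0.44·SD. That is 0.53 (SD 1.2) to 0.62 (SD 1.4) units in every positive patient.

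**The case against.** The strongest reply is that open label describes knowledge of an assigned treatment, and this observational cohort assigns none. The same part of the protocol calls serostatus groups treatment arms and speaks of efficacy endpoints, so the label may be carried-over trial wording. Running the assay in batch after follow-up would fit the text equally well. This stands. A reader might infer that the protocol orders an unmasked assessment, or that the results will be biased. The text supports neither reading: it does not say who sees the result. What remains is that nothing limits access to the result and the only word on the matter points towards openness.

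Second, the size is assumed throughout. This also stands. The protocol gives no SD and no basis for any particular shift, and step 4 shows that modest scoring bias would not by itself produce the planned 17-point gap. The uncorrected test gives the larger error rates, but it is not the test named in the protocol.

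Third, a comparison of the sedimentation rate alone could probe for detection bias in DAS28. It could, but it would not remove the bias, and it says nothing about prescribing.

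Fourth, keeping a laboratory result from prescribers and patients could change the care that an observational study is meant to observe. This stands where the result is part of usual care, and it limits the remedy.

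**Conclusion.** The concern holds as a risk that the plan leaves open. The protocol labels the cohort open label, sets no rule on access to the anti-CarP result, and rests its primary efficacy endpoint on a partly subjective index under a directional hypothesis. Knowledge of status could also affect the prednisone and DMARD endpoints.

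The size of any bias is unknown. The continuity-corrected rates in the table, roughly 6-7% for a 0.1-unit shift and 13-17% for 0.2 against 4.1% with none, show only how sensitive the comparison is. They rest on an assumed normal distribution, SD, 50% base rate and uniform shift. They should not be read as an estimate of this study's error rate, nor as evidence that an observed difference would be an artefact. The point is worth acting on because prevention is cheap and later analysis cannot reliably remove the bias.

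**What to change.** Replace the open-label wording in Study Design with a statement that DAS28 is assessed without knowledge of anti-CarP status, and say how this is achieved. Two ways would serve:

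- stored serum is assayed in batch, with results produced after the DAS28 assessments; or
- the laboratory or data manager holds the research result outside the clinical record until the patient's last DAS28 assessment.

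If the antibody result is used in usual care, it should not be withheld for the study. In that case, record when and to whom it was released, keep the DAS28 assessor unaware of it where possible, and report the prednisone and DMARD comparisons as open to status-driven prescribing.

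If recruitment aims to fill 131 places in each group, having the laboratory report only eligibility is not an adequate safeguard. Once one group is full, eligibility reveals the status of every later recruit. Batch assay after follow-up would leave the group sizes uncontrolled, so the protocol should also say how the 131 per group are reached.

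The cost is a short protocol paragraph, a small data-access task and later availability of a research result. Masking does not itself change the sample size calculation or the visit schedule.
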